9.3.2 Outcomes

9.3.2.1 Primary outcomes

Primary endpoint

- Recorded pneumonia based on 1)ICD-10 code (J12.x-J18.x, J69.0, J84.9, B96.0, J85.1) AND 2) CPT code of chest x-ray(71045-71048) or chest CT(71250,71260,71270,G0297) AND 3) prescription of antibiotics for pneumonia in Korean Guideline) incidence rate per year
- Frequency rate of COPD exacerbation per year
 - Moderate exacerbation: recorded as when COPD patients visited outpatient clinics with an ICD-10 code of COPD and systemic steroid medication and/or antibiotics were prescribed (within the first year after initial prescription of inhalers)
 - Severe exacerbation: when COPD patients visited the emergency room or were admitted to hospital with an ICD-10 code of COPD(*due to COPD worsening*) and were prescribed systemic steroid medication and/or antibiotics (within the first year after initial prescription of inhalers)
- Time to start triple combination therapy ICS/LABA/LAMA)
 - Time to add LAMA in patients with using ICS/LABA or, time to add ICS/LABA in patients with using LAMA before.

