9.3.3 Covariates

Age, sex and history of COPD exacerbation, income status(quartile) or medical health insurance are all matching factors and will thus inherently be accounted for.

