9.7 DATA ANALYSIS

The study population consists of COPD patients that have received LAMA and ICS/LABA treatment. The study consists of three stages: a) identification and extraction of LAMA-exposed and ICS/LABA-

exposed cohort, b) matching between LAMA-exposed and ICS/LABA-exposed and c) descriptive analysis of cohorts and analysis of outcomes.

Detailed methodology for summary and statistical analyses of data generated in this study will be documented in an SAP. The SAP may modify the plans outlined in the protocol; any major modifications of primary endpoint definitions or their analyses would be reflected in a protocol amendment.

For the purpose of this study, analyses will be conducted using SAS statistical software and R. To address the imbalance of potential confounders between LAMA ICS/LABA groups, we matched treatment groups using propensity scores estimated as by multiple logistic regression analysis *based on* as age, sex, socioeconomics status, *Charlson Comorbidity Index*, and asthma, history of COPD exacerbation. Demographics and clinical characteristics will be tabulated. Frequencies and percentages will be presented for categorical variables. For continuous variables, means, standard deviations, and ranges, or medians and inter-quartile ranges, will be reported as appropriate. We used a standardised difference to compare baseline characteristics between COPD patients who were treated with LAMA and those treated with ICS/LABA. The matched Cox proportional hazards regression analyses will be used to estimate hazard ratios (HRs) HRs and 95% confidence intervals (95% CIs) for all outcomes. For (possibly) repeating events (such as *exacerbation event*) *additionally* a Poisson regression model will be fitted for the number of events (taking into account the matching). The cox and Poisson models will be adjusted for unbalanced PS-variables at baseline. Mortality was estimated by the Kaplan-Meier method, and results were compared between groups using the log-rank test.

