9.7.1 Analysis Dataset : Patients selection

The matching between LAMA[Spriva® HandiHaler® Respimat® (Tiotropium Bromide Monohydrate)] and ICS/LABA are performed by sex, age category (5 year spans above 55 years), years since diagnosis of COPD, as available in the database, and propensity score.

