9.7.1.1 Propensity score methodology

The propensity score will model the likelihood among COPD patients of receiving LAMA and ICS/LABA. The model for the propensity score will to the extent possible include the following elements:

- 1) Age and sex
- 2) Socioeconomic status (e.g. income, educational level, single living)
- 3) History of COPD exacerbation
- 4) Charlson Comorbidity Index
- 5) History of asthma

A logistic regression analysis will be performed on the identified COPD patients where treatment with LAMA and ICS/LABA groups is the dependent, dichotomous variable and the independent variables are listed above (age, sex and history of COPD exacerbation et al.). Based on this analysis, the propensity score is calculated for each patient. For subgroup analyses, PS matching and evaluation of its success, as presented below, will be re-done as covariate balance is not automatically maintained in sub-cohorts.

Smoking may be an important confounder in COPD but smoking status is usually not available in the databases at all. If smoking status is confirmed to be available, the data will be analysed with and without smoking status included in the model and the magnitude of the confounding effect assessed (sensitivity analysis).

PS matching will be done in a 1:1 ratio using the nearest-neighbor algorithm, using calipers of width equal to 0.2 of the standard deviation of the logit of the PS (matches of the main exposure sub-cohort and the comparator sub-cohort are formed if the caliper width is not exceeded for the logit of PS). For LAMA-exposed patient to ICS/LABA-exposed patients will be selected within the same matching interval of the propensity score. The distribution of propensity scores will be examined between LAMA-exposed and eligible ICS/LABA-exposed. In the matching procedure, matched comparator sub-cohort patients (ICS/LABA) will be removed from the pool of eligible patients among the comparator sub-cohort so that a matched patient is no longer available for consideration as a potential match for another exposed patient.

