Evaluation of the success of the matching procedure will be based on a standardized difference (detailed below) of a covariate that is less than 0.1 between treatment groups. A standardized difference of a covariate of less than 0.1 between treatment groups in this study indicates a negligible difference in the mean or prevalence of the covariate. If larger standardized differences than 0.1 for some covariates exist after matching, they will be used in post-matching adjustments (i.e. PS-variables with standardized difference >0.1 will be adjusted for in the analyses). Further adjustments can also be made as appropriate in additional models. Based on differences identified through exploratory analysis of baseline variables, we matched individual patients from each cohort (1:1) to ensure comparison of similar patients.

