9.7.2 Main analysis

For the primary effectiveness outcomes incidence rates (events per 1,000patients-years) with corresponding 95% confidence intervals (CI) will be calculated. This will be evaluated by a matched Cox proportional hazards regression model for counting processes, which allow the follow-up time to be divided into several periods and therefore control for baseline and time-dependent covariates, using the full observational period of available data, i.e. up to 11 years of follow up. The Cox proportional hazards regression will take into account the fact that individual matching (1:1) will be performed by considering the exposed patient and his/her matched controls as one stratum and including this as a stratum in the Cox proportional hazards model. Additional variables will be included in the model if available. The cumulative incidence plots will be accompanied by number of patients at risk at different time points during follow-up. For (possibly) repeating events (such as exacerbation event) additionally a Poisson regression model will be fitted for the number of events (taking into account the matching). Time in the study will be included as an offset variable in the model. The cox and Poisson models will be adjusted for unbalanced PS-variables at baseline.

The outcome will be analyzed separately for each:

- 1) Primary outcome
 - Comparison of pneumonia incidence in COPD patients using LAMA and ICS/LABA
 - Comparison of exacerbations frequency and rate in COPD patients using LAMA and ICS/LABA : moderate or severe exacerbation

Proprietary confidential information © 2022 Boehringer Ingelheim International GmbH or one or more of its affiliated companies

[figure not shown]
- Comparison of time to start triple combination therapy (time from initial 'LAMA mono' or ICS+LABA' to 'LAMA+LABA+ICS' combination) in COPD patients using LAMA and ICS/LABA

2) Secondary outcome

- Comparison of all-cause mortality differences in COPD patients using LAMA and ICS/LABA
- Comparison of lung cancer incidence in COPD patients using LAMA and ICS/LABA
- Comparison of health care utilization: Medical cost / No. of prescriptions, visits and hospitalizations (hospitalization mainly due to severe exacerbation of COPD)

Health care utilization

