9.3.2 Outcomes? (e.g. International Classification of Diseases (ICD), Medical Dictionary for Regulatory Activities (MedDRA))				9.3.2
9.3.3 Covariates and other characteristics?				9.3.3
9.4 Is a linkage method between data sources described? (e.g. based on a unique identifier or other)				9.3-9.6

Comments:

--

Section 10: Analysis plan	Yes	No	N/A	Section Number
10.1 Are the statistical methods and the reason for their choice described?				9.7
10.2 Is study size and/or statistical precision estimated?				9.5, 9.7
10.3 Are descriptive analyses included?				9.7
10.4 Are stratified analyses included?				
10.5 Does the plan describe methods for analytic control of confounding?				9.7
10.6 Does the plan describe methods for analytic control of outcome misclassification?				9.3.3
10.7 Does the plan describe methods for handling missing data?				
10.8 Are relevant sensitivity analyses described?				9.7.3

Comments:

There is no missing data as we are using national health claim data source and this is universal health plan covering all Korean population

Section 11: Data management and quality control	Yes	No	N/A	Section Number
11.1 Does the protocol provide information on data storage? (e.g. software and IT environment, database maintenance and anti-fraud protection, archiving)				9.6
11.2 Are methods of quality assurance described?				9.8

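### The visible text names no overdispersion-tolerant variance for the Poisson model of exacerbation counts; with pair strata or model-based standard errors, its 95% CIs would be too narrow wherever patients differ within pairs

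*Combined protocol and SAP*

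**What the plan says.** Section 9.3.2.1 lists the yearly frequency of COPD exacerbation among the primary endpoints and limits both the moderate and the severe definition to events "within the first year after initial prescription of inhalers".

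Section 9.7.2 evaluates the primary outcomes by a matched Cox counting-process model. For repeating events it then says that "additionally a Poisson regression model will be fitted for the number of events (taking into account the matching"). The Abstract and section 9.7 say the same. Section 9.7.2 adds time in study as an offset and adjustment for propensity-score variables left unbalanced. For Cox it says how matching enters (each pair is a stratum) and gives a follow-up of up to 11 years. For Poisson it says neither how matching enters nor how the variance is obtained. The visible text has no robust variance, scale parameter, dispersion check or negative binomial model.

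Section 9.7 states: "Detailed methodology for summary and statistical analyses of data generated in this study will be documented in an SAP". No separate SAP is among the documents. The contents list has a blacked-out entry after 9.7.2, and the Annex 2 checklist, at "10.8 Are relevant sensitivity analyses described", points to a section 9.7.3 that is not visible.

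On what pairs have in common, section 9.3.3 says: "Age, sex and history of COPD exacerbation, income status(quartile) or medical health insurance are all matching factors". Section 9.7.1 matches on sex, five-year age band, "years since diagnosis of COPD, as available in the database, and propensity score". Section 9.7.1.1 lists "History of COPD exacerbation" as an input to that score. On residual imbalance it says "PS-variables with standardized difference >0.1 will be adjusted for in the analyses", and then allows further adjustment in additional models.

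**The concern.** A Poisson model takes the variance of a count to equal its mean. Patients usually differ in their tendency to exacerbate beyond what covariates explain, and the counts then vary more than that. Conditioning on the pair, the Poisson analogue of the Cox stratum, removes only the part of this variation common to both members. Two patients with the same sex, age band, years since diagnosis and a similar score can still have different exacerbation histories. A well-balanced predictor also need not enter the Poisson mean, because the planned adjustment is triggered by imbalance. Some unshared overdispersion is therefore plausible.

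The requirement to take the matching into account is met equally by a pair-clustered sandwich, which handles the problem, and by a pair-conditional model with model-based standard errors, which does not. At stake is the stated precision of the LAMA versus ICS/LABA rate ratio, since this is the only model in the visible text described as fitted to the number of events. The documents give no alpha or decision rule, so the harm is to the reported interval, not to a formal test.

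**Working it through.** The plan gives no standard error, interval width, exacerbation rate or dispersion, so there is no figure to reproduce.

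**Inputs from the documents.** 1:1 matching (9.7.1.1); at least 5,000 patients per arm, a feasibility figure (9.5), taken here as n = 5,000 pairs; 95% intervals (9.7); first-year counting window (9.3.2.1).

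**Assumed inputs.** Mean count μ from 0.3 to 1.5 per year; variance k of the patient-level rate multiplier from 0.25 to 2; ρ, the share of that heterogeneity common to the pair, from 0 to 1.

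**Formula (equal follow-up, no treatment effect).** Each arm total has variance n(μ + kμ²), and the two totals have covariance nρkμ². Hence

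Var(log RR) ≈ [2n(μ + kμ²) − 2nρkμ²]/(nμ)² = (2/(nμ)) × VIF, with VIF = 1 + kμ(1 − ρ).

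Plain Poisson and pair-conditional Poisson both report 2/(nμ). Actual coverage is 2Φ(1.96/√VIF) − 1.

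| μ, k | ρ = 0: VIF, coverage | ρ = 0.5 | ρ = 0.75 | ρ = 1 |
|---|---|---|---|---|
| 0.3, 0.25 | 1.075, 94.1% | 1.0375, 94.6% | 1.019, 94.8% | 1, 95% |
| 1, 1 | 2, 83.4% | 1.5, 89.0% | 1.25, 92.0% | 1, 95% |
| 1.5, 2 | 4, 67.3% | 2.5, 78.5% | 1.75, 86.2% | 1, 95% |

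**On the interval scale.** For μ = 1, k = 1 and RR = 1, the reported SE is √(2/5000) = 0.020, giving 0.962 to 1.040. With half shared the SE should be 0.020 × √1.5 = 0.0245, giving 0.953 to 1.049. With none shared it should be 0.020 × √2 = 0.0283, giving 0.946 to 1.057.

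**Unequal follow-up, by simulation.** Gamma heterogeneity, 5,000 pairs, 3,000 replicates, one year, 25% censored uniformly. Type I error for model-based / pair-conditional / pair-clustered sandwich:

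| μ, k | ρ = 0 | ρ = 0.5 | ρ = 1 |
|---|---|---|---|
| 0.3, 0.25 | 0.063 / 0.059 / 0.057 | 0.054 / 0.049 / 0.051 | 0.050 / 0.048 / 0.050 |
| 1, 1 | 0.156 / 0.153 / 0.047 | 0.111 / 0.107 / 0.047 | 0.054 / 0.046 / 0.044 |
| 1.5, 2 | 0.296 / 0.290 / 0.043 | 0.217 / 0.197 / 0.047 | 0.079 / 0.055 / 0.050 |

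The clustered sandwich stays between 0.043 and 0.057. At full sharing and unequal follow-up the plain model is still slightly off in the worst assumed case: 1 − 0.079 = 92.1% coverage.

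**Pair random intercept.** With unshared k = 1 plus a pair component of 0.3 (2,000 pairs, 200 replicates), the model SE was 0.0316 against an empirical 0.0431, with 84.5% coverage. It too absorbs only the shared part.

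**Other variances.** At μ = 1 and k = 1, equal follow-up, a patient-level sandwich and a quasi-Poisson scale each covered 95.8% with nothing shared and 99.5% with everything shared: safe, but too wide when pairs share much. A negative binomial model and a pair bootstrap were not simulated.

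**Window.** VIF grows with the mean count. Over four years at 1 event per year, k = 1 and half shared, VIF = 1 + 1 × 4 × 0.5 = 3 and coverage is 2Φ(1.96/√3) − 1 = 74.2%.

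**The case against.** The strongest reply is that this argues from silence. A variance estimator is ordinary SAP detail, the plan defers to an SAP, a subsection is redacted, and taking the matching into account may mean clustering on the pair. That stands to this extent: the documents show wording that permits an invalid interval, not a decision to use one. A reader might infer that the plan has chosen a wrong method; the text does not support that.

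The Poisson model is also additional to Cox, and section 9.7.2 names Cox as the evaluation of the primary outcomes. That limits the consequences but does not make the Poisson interval correct.

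Four stronger readings are tempting and do not hold.

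- **Only a pair-clustered sandwich is safe.** A patient-level sandwich, quasi-Poisson scale, negative binomial model or pair bootstrap would also allow for overdispersion.
- **Balanced predictors are barred from the Poisson mean.** Section 9.7.1.1 permits further adjustment in additional models; it does not require it.
- **Sections 9.3.3 and 9.7.1 contradict each other on matching factors.** The factors in 9.3.3 can enter through the propensity score. What remains unclear is how closely pairs agree on exacerbation history.
- **The Poisson counts run to 11 years.** That period stands in the Cox sentence, and time in study as offset is compatible with a one-year count.

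Finally, every magnitude is assumed. That is correct, and the lowest coverage combines the highest mean, the highest k and no sharing.

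**Conclusion.** The concern holds as a conditional statement about the visible text. A primary count endpoint has a Poisson analysis with no overdispersion-tolerant variance named. If pair strata or model-based standard errors are used, heterogeneity not shared within pairs makes the 95% CIs too narrow.

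The size rests on assumed rates, dispersion and sharing. At mean 1 per year and k = 1, coverage runs from about 83% (none shared) to 92% (three quarters shared). At mean 0.3 and k = 0.25 the loss is negligible. With full sharing, coverage is 95% for the pair-conditional model or under equal follow-up, while the plain model can fall to about 92% in the worst assumed case when follow-up is unequal. The change should be made because the wording allows the error and the remedy is cheap. It does not show that any reported result would be wrong.

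**What to change.** In section 9.7.2, state that the number of exacerbations is analysed by a marginal Poisson model with log time at risk as offset, and that its confidence intervals use sandwich standard errors clustered on the matched pair. Report Pearson chi-square/df. The ratio of clustered to model-based SE is a useful addition, because in the simulations the Pearson statistic was about the same (1.07, 1.87 and 3.62 for the three settings) whatever share the pairs had in common. State that counts and offset cover the same period, reconciling the first-year definition in 9.3.2.1 with the time-in-study offset in 9.7.2, and say which factors are matched directly and which only through the score. If the SAP or the redacted subsection already sets a suitable variance, a cross-reference in 9.7.2 is enough.

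The cost is a few sentences and a standard option in SAS and R. Over the assumed one-year range with equal follow-up, intervals widen by √1.075 = 1.04 to √4 = 2.0 if pairs share nothing, and by √1.0375 = 1.02 to √2.5 = 1.58 if they share half. The point estimate is unchanged if a marginal model was intended. If a pair-conditional model was intended, the estimate changes modestly: in the simulations the two log rate ratios differed with an SD of 0.008 to 0.011, against a sampling SD of 0.018 to 0.043.

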9.2 SETTING

The study will be conducted in a general practice setting, Korea National Health Insurance claim data & mortality data from the Bureau of Statistics, which includes computerized medical records of more than half million patients in South Korea. The maximal observation period will be from Jan 2005 to Apr 2016.

- Inclusion criteria
 - Diagnosed with COPD [**based on ICD-10 code(J43.x-44.x except J430), as the primary or within the fourth secondary diagnosis and initiated LAMA or ICS/LABA more than twice a year from Jan 1, 2005 to Apr 30 2016**].
 - Age >55 years old as of 2005 when enroll started
- Exclusion criteria
 - Prescription history with any long acting bronchodilator for maintenance therapy (the patient should be inhaler naïve) from 2002 to 2005.
 - Prescription history with ipratropium bromide
 - Prescription history with Leukotriene receptor antagonist(LTRA) or ICS
 - Prescription history of LABA/LAMA FDC
 - Patients with lung cancer, IPF, ILD or lung transplantation at the time of COPD diagnosis

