9.12 BIAS

This study will include users of LAMA and ICS/LABA. Immortal time bias will be minimal, as the follow-up will begin at the initiation of drug use. Adherence to drug use will be unknown.

Comparing the outcomes between users of LAMA and ICS/LABA will decrease confounding by indication, as the comparison group will have a similar indication to drug use than the patients in the LAMA-exposed cohorts.

The compared sub-cohorts will be matched on the basis of PS. The PS will be computed on the basis of a wide range of covariates related to sociodemographic characteristics, history of exacerbation, other comorbidities, and prior/concomitant use of other drugs. The PS matching will decrease the systematic differences between the sub-cohorts and, thus, decrease confounding.

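### The exacerbation endpoint counts first-year events only, but the main analysis uses up to 11 years of follow-up and a Poisson offset with no stated cap, so events and person-time have no agreed window

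*Combined protocol and SAP*

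**What the plan says.** Section 9.3.2.1 (Primary outcomes) lists "Frequency rate of COPD exacerbation per year" as a primary endpoint. The moderate and the severe definition both end with the same limit: "within the first year after initial prescription of inhalers". In that section the limit applies to exacerbations only, not to pneumonia or to time to triple therapy.

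Section 9.7.2 (Main analysis) sets one rule for all primary outcomes. It starts with crude rates: "For the primary effectiveness outcomes incidence rates (events per 1,000patients-years) with corresponding 95% confidence intervals (CI) will be calculated". It then specifies a matched Cox model, "using the full observational period of available data, i.e. up to 11 years of follow up". For repeating events, with exacerbation as the example, "additionally a Poisson regression model will be fitted for the number of events (taking into account the matching"). On person-time for that model it says only: "Time in the study will be included as an offset variable in the model".

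Section 9.12 (Bias) fixes the start of the clock: "the follow-up will begin at the initiation of drug use". Section 9.2 (Setting) fixes the calendar limits: "The maximal observation period will be from Jan 2005 to Apr 2016". Sections 9.3 and 9.7 defer detailed definitions and methods to an SAP, but the document supplied contains no SAP definition of the offset or of the person-time for the exacerbation rates.

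**The concern.** A rate needs events and person-time from the same window. Here the events carry a one-year limit, the Cox follow-up runs to 11 years, and the Poisson offset has no stated limit. Three readings are open:

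- **(a)** Events and person-time are both confined to the first year. This is coherent.
- **(b)** Both run over full follow-up. This is coherent, but contradicts the endpoint definition.
- **(c)** First-year events are divided by total follow-up. This is wrong, because the time after year 1 enters the denominator with no chance of adding to the numerator.

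Readings (a) and (b) are different estimands: the first-year rate and the all-period rate. Readings (a) and (c) could give annual rates several-fold apart from the same data. The rate per year is the primary endpoint as named, and the crude rates and the count model are where it is estimated.

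**Working it through.** **The plan's own figure.** 1 January 2005 to 30 April 2016 is 11.33 years, which agrees with the stated maximum of up to 11 years. A patient who starts early can therefore have far more than one year of follow-up.

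**Size of the error in the rate under (c).** Let T be a patient's follow-up in years and r the true annual rate. Expected first-year events are r × min(T, 1). Divided by total time, the reported rate is r × mean(min(T, 1)) / mean(T), so the understatement is

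fold = mean(T) / mean(min(T, 1)).

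If everyone completes a first year, this is simply mean follow-up in years. For a common T and a true rate of 1.0 per year, the reported rate is 1/2 = 0.50 at T = 2, 1/5 = 0.20 at T = 5 and 1/11.33 = 0.088 at T = 11.33.

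The protocol gives no distribution of start dates and no exit rate, so both are assumptions. T is the smaller of (11.33 − entry time) and an exit time with constant hazard. Seven uptake curves were used: even uptake, three weighted to early starts and three weighted to late starts.

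| Exit hazard per year | Fold, even uptake | Fold, range over curves |
|---|---|---|
| 3% | 5.39 | 3.86–6.79 |
| 6% | 4.93 | 3.62–6.13 |
| 10% | 4.41 | 3.34–5.40 |
| 20% | 3.48 | 2.81–4.11 |
| 30% | 2.88 | 2.43–3.30 |

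The overall range is about 2.4 to 6.8, or about 2.9 to 6.9 if a complete first year is required. Example with even uptake and a 6% hazard: a true 500 per 1,000 patient-years becomes 500 / 4.93 = 101. A simulation of the same case (5,000 per arm) gave 101.6 under (c), 500.5 under (a) and 500.1 under (b).

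**Check with a fitted model.** The true rate was 1.0 per year, with 5,000 per arm and T uniform on 1–11 years (mean 6) in both arms. A Poisson model for first-year events with total time as offset returned 0.164, close to 1/6. With the offset capped at one year it returned 0.998.

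**Rate ratio under (c), no true effect.**

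- Same follow-up distribution in both arms: 0.99 (95% CI 0.95–1.03), so no distortion.
- LAMA follow-up uniform on 1–9 years, ICS/LABA on 1–11: LAMA to ICS/LABA ratio 1.23 (1.19–1.28). With the capped offset it is 1.03 (0.99–1.07).
- Equal means but different spread: an unconditional Poisson model gives 1.00. A model conditional on the matched pair does not, because it depends on how each pair's two follow-up times compare. With equal true rates and complete first years it settles at the θ for which the mean of θT₁ / (θT₁ + T₀) is 1/2. For T₁ = 5 and T₀ uniform on 1–9, that is (5θ/8) × ln[(5θ + 9)/(5θ + 1)] = 0.5, so θ = 0.88. With T₁ uniform on 3–7, simulation gives about 0.91.

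Sections 9.7.1 and 9.7.1.1 match on sex, age band, years since diagnosis and a propensity score built from age, sex, socioeconomic status, exacerbation history, comorbidity index and asthma. Date of treatment start is not among them, so matching does not ensure equal follow-up.

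**Cox model.** The partial likelihood uses only the risk sets at event times. If only first-year events count, time after year 1 contributes nothing and the hazard ratio is unchanged.

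**The case against.** The strongest reply is that the plan never states the faulty calculation. The 11-year phrase is in the Cox sentence; the Poisson sentence names no period. An offset ordinarily means the time over which the counts accrue, which leads to (a) or (b). An SAP is announced, and defining an offset is the kind of detail it would hold. This stands as far as it goes: (c) is one of three readings, and a reader who infers that the plan prescribes it goes beyond the text. It does not remove the conflict. The first-year limit and the full-period rule both apply to exacerbations as a primary outcome, and even a careful analyst must choose between (a) and (b).

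A second reply is that the Cox comparison is the main evaluation and the Poisson model an addition. That also stands, and the Cox result is not at risk. But the endpoint is named as a rate, and the Cox model does not estimate it.

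A third reply is that the size is assumed throughout. That is correct. Reading 30% as an annual probability lowers the minimum to about 2.3, and a hazard of 0.5 gives 2.0–2.4. The direction needs only that some patients are followed beyond one year.

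**Conclusion.** The concern holds as an unreconciled window for a primary endpoint, and it should be settled before analysis. Under the mismatched reading, the crude annual exacerbation rate and the rate from an unconditional Poisson model are too low by mean(T)/mean(min(T, 1)). That is about 2.4- to 6.8-fold under the assumed uptake curves and constant exit hazards of 3–30% per year. A pair-conditional Poisson model yields no absolute rate, so for that model only the ratio is at issue.

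A reader might infer that the LAMA versus ICS/LABA comparison is biased. The documents do not support that. The Poisson ratio is distorted only if reading (c) is used and the follow-up distribution differs between arms (for a pair-conditional model, even at equal means). The omission of start date from the matching leaves this possible, but no figure in the protocol shows a difference. The Cox hazard ratio for first-year exacerbations is unaffected.

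**What to change.** Reconcile Sections 9.3.2.1 and 9.7.2 so that exacerbation events and person-time share one window. Either:

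- **(a)** Keep the first-year definition. Use log(time at risk within the first year after the initial prescription, truncated at death or end of data) as the Poisson offset, and the same person-time for the crude rates. State that the 11-year follow-up does not apply to exacerbations.
- **(b)** Revise Section 9.3.2.1 to count exacerbations over full follow-up in the crude-rate, Poisson and Cox analyses, with total time as the offset.

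State which is primary. Section 9.7 lets the SAP modify the plan but sends major changes to primary endpoints or their analyses to a protocol amendment, and Section 9.8 asks for all changes to be recorded as amendments. The choice should therefore be documented that way.

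Neither option needs new data. Option (a) is a short clarification, but it leaves later exacerbations unused. Option (b) uses them, but it changes the window of a primary endpoint, including the events that enter the Cox model.
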